#### 12.6.5 Safety Endpoint Analysis

The following analyses will be carried out on the Safety Populations. ACTitouch® treated subjects will be compared with multi-layer bandaging treated subjects in terms of:

- the difference in the incidence of ulcer-related adverse events (defined as ulcer infections, maceration, allergic reaction to dressing, or hospitalization for worsening VLU) at 16 weeks using the Kruskal-Wallis test.
- the difference in the incidence of ulcer infections at 16 weeks using the Kruskal-Wallis test.
- the difference in the incidence of ulcer maceration at 16 weeks using the Kruskal-Wallis test.
- the difference in the incidence of allergic reactions to dressing at 16 weeks using the Kruskal-Wallis test.
- the difference in the incidence of hospitalization for worsening VLU at 16 weeks using the Kruskal-Wallis test.

#### 12.7 Interim Analysis:

There will be a formal interim analysis of the primary endpoint when 50% of the subjects have completed the 16 week treatment phase, defined as completing all 16 weeks, healed or withdrew prior to the 16 week visit or healing. At this interim visit, comparison of the percentage ulcer area reduction between ACTitouch® treated subjects with multi-layer bandaging treated subjects will be made using the same ANOCOVA model as above. The DSMB will not recommend stopping the study for overwhelming efficacy based on the comparison of the ACTitouch® doses versus control (multi-layer bandaging). Nevertheless, due to the interim look, an O'Brien-Fleming-type alpha-penalty for the final analysis will be taken; and the final one-sided alpha will be 0.0249

The DSMB will be provided with conditional power of obtaining non-inferiority of ACTitouch to control with respect to mean percent ulcer healing by the end of the study. This conditional power is calculated according to the following formula:

$$CP_{\delta}(n_2, Z_{\alpha}|Z_1) = 1 - \Phi \left[ \frac{Z_{\alpha} \sqrt{2(n_1+n_2)} - Z_1 \sqrt{2n_1} - n_2(\delta - \delta_{\Delta})}{\sqrt{2n_2}} \right]$$

where:

$n_1$  – sample size per arm at interim;

$n_2$  – sample size per arm in second stage (from interim to final analysis) as originally planned;

$\Delta$  – non-inferiority margin;

$\delta_{\Delta} = \Delta/\sigma$  ;

$\sigma^2$  – assumption of true variance of treatment effects pooled across arms (estimated from the interim data);  
 $\delta$  – assumption of true effect size= $(\mu_C - \mu_T)/\sigma$  (this will be set to 0);  
 $z_1$  – non-inferiority test statistic calculated at the interim analysis;  
 $z_\alpha$  –  $\alpha$  percentile of the standard normal distribution ( $\alpha =$  one-sided 0.0249);  
 $z_\beta$  –  $\beta$  percentile of the standard normal distribution;  
 $\Phi[\ ]$  – the standard normal cumulative distribution function.

### 13.0 Compensation:

Study subjects may be compensated for their time and travel associated with participation in this study.

### 14.0 Publication Plan:

All information obtained during the conduct of the study will be considered to be confidential and is property of Tactile Medical. Written permission from the Sponsor is required before disclosing any information related to this study. All publications (e.g. manuscripts, abstracts, and presentations) based on this study must be submitted to the Sponsor for review and approval before submission or according to the individual site clinical trial agreement.

## 16.0 Appendices

TACTILE TABLES - SAP

In this abbreviated Statistical Analysis Plan (SAP), we present the tables/figures to be produced for TACTILE. We retain the paragraph numbering from the original SAP.

8.1 Patient Accountability

The number and percentage of randomized and withdrawn patients will be presented by treatment group (Table 14.1.1). The number and percentage of enrolled patients prematurely discontinuing the study will also be presented by treatment group together with the reason for withdrawal. Patient accountability will also be presented by site stratified by treatment group (Table 14.1.2).

8.2 Safety Analyses

Descriptive statistics and appropriate tests will be used to summarize and compare the safety parameters between treatment groups. All safety analyses will be performed on the safety population. Treatment group comparisons will assess the significance of the difference between treatment and control groups.

8.2.1 Adverse Events

Adverse events will be coded according to pre-specified Tactile internal codes. Adverse events will be summarized by severity, outcome, causality and seriousness (i.e., SAE) and stratified by treatment group (Table 14.3.1). For subjects with more than one event, the event with the highest level of severity, outcome or causality, seriousness, respectively, will be reported. The number and percentage of subjects with an event by the internal Tactile AE codes will be compared by treatment group (Tables 14.3.2). Subjects with more than one event by internal Tactile code will be counted only once. All AEs will be listed, sorted by treatment group, subject identification, and date of the AE (Table 16.2.7.1). Data presented will include: causality, severity, seriousness, outcome, verbatim description, internal Tactile codes.

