Control Group: Subjects assigned to multi-layer bandaging must wear the bandaging 24 hours a day except during clinic visits when the limb is being assessed by the study staff.

Follow Up Period

All subjects assigned to the ACTitouch arm who heal during the 16 week treatment period will be followed for 3 months post VLU healing. These subjects will be instructed to continue to use the ACTitouch device as outlined in the 16 week treatment period [sustained mode during all wakeful hours (12 hours each day) and IPC mode for 2 hours daily]. Subjects will be instructed to remove the ACTitouch for bathing and when driving or operating machinery, and reapplied immediately after these activities.

5.4 Study Timetable:

Task	Months				
	1-6	7-12	13-18	19-24	24-30
Identify Sites	X				
IRB/Regulatory	X				
Enrollment		X	X		
Treatment		X	X	X	X
Data Entry		X	X	X	X
Data Analysis					X

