**6.0 Study Visit Summaries:**

6.1 Screening Visit:

At this visit, the patient will be asked to provide written informed consent and inclusion and exclusion criteria will be evaluated to ensure that the patient meets all entrance criteria. See the Study Schedule of Activities section 7.17 for visit activities. After the informed consent process is complete, the subject will begin the run-in phase of the study.

Subjects may be enrolled if they are on a current Pentoxifylline regimen, but Investigators should not start patients on Pentoxifylline during the trial if the patient is not taking the drug at enrollment.

6.2 Run-in Visit:

There could be up to 4 visits during the run in phase, 3 visits if the Screening and Baseline visits occur on the same day. The visit schedule is as follows Screening/Baseline; Run-in Week 1 and Randomization ( $\pm 2$  days). The subjects will follow the treatment regimen outlined in section 7.17. At each visit the study staff will access the ulcer. If the subject meets any of the exclusion criteria listed in section 5.2.3 at the Randomization Visit the subject will be excluded from the study.

6.3 Randomization Visit:

At the randomization visit the subject will undergo procedures as outlined in the Study Schedule of Activities table in section 7.17.

The subject will leave the randomization visit with:

- Schedule for the next study visit (if possible, follow-up visits should be scheduled at the same time of day)
- Instructions on use and application of the assigned study apparatus, as applicable
- Diary and instructions to record daily activity
- Contact information and instructions to call if any problems arise

6.4 Treatment Visits (Weeks 1-16 or healed):

Investigational Group: Subjects will be seen in clinic at weeks 1, 2, 4, 6, 9, 12, 16 ( $\pm 2$  days) for 16 weeks or until the VLU is completely healed, as defined by complete closure with no open area or exudate. At the visits the subject will undergo the procedures as outlined in the Study Schedule of Activities table in section 7.17.

Control Group: Subjects will complete weekly visits for 16 weeks or until the VLU is completely healed, as defined by above. At the weekly visits the subject will undergo procedures as outlined in the Study Schedule of Activities table in section 7.17.

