#### 9.3 Adverse Event Reporting:

Investigators will be responsible for reporting the following pre-defined adverse events regardless of severity, to Tactile Medical in a timely manner:

- New or worsening ulceration

- Clinically worsened or new onset heart failure
- Increase in leg swelling greater than 20%
- Skin irritation/blistering
- Infection of the study limb(s)
- Other – an AE that according to the investigator’s opinion is significant and requires reporting to Tactile Medical but doesn’t necessarily meet the definition of the pre-defined AEs or an SAE

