APPENDIX: DATA TABLES

TACTILE TABLES - SAP

Sponsor: Tactile Medical Systems
Protocol: 6010

page 1 of x

Table 14.1.1 Patient Disposition

ITT sample

	1.5cm<=size<=12cm				12cm<size<= 50cm			
	1<=age<6 months		1<=age<6 months		6<=age<=24 months		6<=age<= 24 months	
	Treatment (N)	Control (N)	Treatment (N)	Control (N)	Treatment (N)	Control (N)	Treatment (N)	Control (N)
Randomized	xx/xx(xxx.x%)	xx/xx(xxx.x%)	xx/xx(xxx.x%)	xx/xx(xxx.x%)	xx/xx(xxx.x%)	xx/xx(xxx.x%)	xx/xx(xxx.x%)	xx/xx(xxx.x%)
Safety	xx/xx(xxx.x%)	xx/xx(xxx.x%)	xx/xx(xxx.x%)	xx/xx(xxx.x%)	xx/xx(xxx.x%)	xx/xx(xxx.x%)	xx/xx(xxx.x%)	xx/xx(xxx.x%)
Completed	xx/xx(xxx.x%)	xx/xx(xxx.x%)	xx/xx(xxx.x%)	xx/xx(xxx.x%)	xx/xx(xxx.x%)	xx/xx(xxx.x%)	xx/xx(xxx.x%)	xx/xx(xxx.x%)
Discontinued	xx/xx(xxx.x%)	xx/xx(xxx.x%)	xx/xx(xxx.x%)	xx/xx(xxx.x%)	xx/xx(xxx.x%)	xx/xx(xxx.x%)	xx/xx(xxx.x%)	xx/xx(xxx.x%)
Primary Reason for Discontinuation:								
Adverse Event	xx/xx(xxx.x%)	xx/xx(xxx.x%)	xx/xx(xxx.x%)	xx/xx(xxx.x%)	xx/xx(xxx.x%)	xx/xx(xxx.x%)	xx/xx(xxx.x%)	xx/xx(xxx.x%)
Protocol Violation	xx/xx(xxx.x%)	xx/xx(xxx.x%)	xx/xx(xxx.x%)	xx/xx(xxx.x%)	xx/xx(xxx.x%)	xx/xx(xxx.x%)	xx/xx(xxx.x%)	xx/xx(xxx.x%)
Lost to Follow-up	xx/xx(xxx.x%)	xx/xx(xxx.x%)	xx/xx(xxx.x%)	xx/xx(xxx.x%)	xx/xx(xxx.x%)	xx/xx(xxx.x%)	xx/xx(xxx.x%)	xx/xx(xxx.x%)
Other	xx/xx(xxx.x%)	xx/xx(xxx.x%)	xx/xx(xxx.x%)	xx/xx(xxx.x%)	xx/xx(xxx.x%)	xx/xx(xxx.x%)	xx/xx(xxx.x%)	xx/xx(xxx.x%)

TACTILE TABLES - SAP

Sponsor: Tactile Medical Systems
 Protocol: 6010

page 1 of x

Table 14.1.2 Patient Disposition By Site
 ITT sample

	Treatment N(%) ^b	Control N(%) ^b	Total N(%) ^b
xxxx	xx/xx(xxx.x%)	xx/xx(xxx.x%)	xx/xx(xxx.x%)
xxxx	xx/xx(xxx.x%)	xx/xx(xxx.x%)	xx/xx(xxx.x%)
xxxx	xx/xx(xxx.x%)	xx/xx(xxx.x%)	xx/xx(xxx.x%)
xxxx	xx/xx(xxx.x%)	xx/xx(xxx.x%)	xx/xx(xxx.x%)
xxxx	xx/xx(xxx.x%)	xx/xx(xxx.x%)	xx/xx(xxx.x%)

Note: denominator of all percentages is number randomized by group

TACTILE TABLES - SAP

Sponsor: Tactile Medical Systems
Protocol: 6010

page 1 of Y

Table 14.3.1 Safety Analysis: Summary Incidence of Adverse Events
Safety sample

Condition	Treatment N(%)	Control N(%)	P-value
Safety Analysis Set	xx	xx	
Patients with Adverse Events	xx(xxx.x%)	xx(xxx.x%)	x.xxx
Patients with AEs by Severity ^a			
No Event	xx(xxx.x%)	xx(xxx.x%)	x.xxx
Mild	xx(xxx.x%)	xx(xxx.x%)	
Moderate	xx(xxx.x%)	xx(xxx.x%)	
Severe	xx(xxx.x%)	xx(xxx.x%)	
Patients with AEs by Causality ^a			
Definitely related	xx(xxx.x%)	xx(xxx.x%)	x.xxx
Probably related	xx(xxx.x%)	xx(xxx.x%)	

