Possibly related	xx(xxx.x%)	xx(xxx.x%)	
Not related	xx(xxx.x%)	xx(xxx.x%)	
No Event	xx(xxx.x%)	xx(xxx.x%)	
Outcome			
No Event	xx(xxx.x%)	xx(xxx.x%)	x.xxx
Resolved	xx(xxx.x%)	xx(xxx.x%)	
Resolved w/ sequelae	xx(xxx.x%)	xx(xxx.x%)	
Continuing	xx(xxx.x%)	xx(xxx.x%)	
Lost to follow-up	xx(xxx.x%)	xx(xxx.x%)	
Death	xx(xxx.x%)	xx(xxx.x%)	

TACTILE TABLES - SAP

Condition	Treatment N(%)	Control N(%)	P-value
Patients with SAEs	xx(xxx.x%)	xx(xxx.x%)	x.xxx
Patients Discontinued due to AE	xx(xxx.x%)	xx(xxx.x%)	x.xxx

NOTE: P-value based on Kruskal-Wallis test controlling for stratification. Denominator is the number of patients in the Safety Analysis Set.
^aPatients experiencing more than one adverse event are counted under the maximum severity experienced across events.

TACTILE TABLES - SAP

Sponsor: Tactile Medical Systems
 Protocol: 6010

page 1 of Y

Table 14.3.2 Safety Analysis: Incidence of Adverse Events by Internal AE Code
 Safety sample

Internal AE Code	Treatment N(%)	Control N(%)	p-value ^a
Patients with Adverse Events	xx(xxx.x%)	xx(xxx.x%)	xxxx
AE_CODE XX	xx(xxx.x%)	xx(xxx.x%)	x.xxx
AE_CODE XX	xx(xxx.x%)	xx(xxx.x%)	x.xxx
AE_CODE XX	xx(xxx.x%)	xx(xxx.x%)	x.xxx
AE_CODE XX	xx(xxx.x%)	xx(xxx.x%)	x.xxx
AE_CODE XX	xx(xxx.x%)	xx(xxx.x%)	x.xxx
AE_CODE XX	xx(xxx.x%)	xx(xxx.x%)	x.xxx
AE_CODE XX	xx(xxx.x%)	xx(xxx.x%)	x.xxx
AE_CODE XX	xx(xxx.x%)	xx(xxx.x%)	x.xxx
AE_CODE XX	xx(xxx.x%)	xx(xxx.x%)	x.xxx
AE_CODE XX	xx(xxx.x%)	xx(xxx.x%)	x.xxx

Note: A patient experiencing multiple incidences of an event with the same internal AE code is counted only once.
^a P-value calculated from CMH Test.

TACTILE TABLES - SAP

Sponsor: Tactile Medical Systems
 Protocol: 6010

page 1 of Y

Table 16.2.7.1 Listing of Adverse Events
 Safety sample

Treatment Group	Patient ID	Onset Date (Study Day)	Stop Date (Study Day)	Internal AE Code	Serious	Duration	Severity	Causality	Outcome
xxx	xx	ddmmyy (xx)	ddmmyy(xx)	xx	xx	xx	xx	xx	xx
xxx	xx	ddmmyy (xx)	ddmmyy(xx)	xx	xx	xx	xx	xx	xx
xxx	xx	ddmmyy(xx)	ddmmyy(xx)	xx	xx	xx	xx	xx	xx
xxx	xx	ddmmyy(xx)	ddmmyy(xx)	xx	xx	xx	xx	xx	xx
xxx	xx	ddmmyy(xx)	ddmmyy(xx)	xx	xx	xx	xx	xx	xx
xxx	xx	ddmmyy(xx)	ddmmyy(xx)	xx	xx	xx	xx	xx	xx
xxx	xx	ddmmyy(xx)	ddmmyy(xx)	xx	xx	xx	xx	xx	xx
xxx	xx	ddmmyy(xx)	ddmmyy(xx)	xx	xx	xx	xx	xx	xx
xxx	xx	ddmmyy(xx)	ddmmyy(xx)	xx	xx	xx	xx	xx	xx

TACTILE TABLES - SAP

Sponsor: Tactile Medical Systems
Protocol: 6010

page 1 of Y

Table 14.3.3 Safety Analysis: Incidence of Ulcer-Related Adverse Events at 16 Weeks
Safety sample

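### Tables 14.3.1 and 14.3.2 test crude adverse-event percentages with no counting window, although only healed ACTitouch subjects are followed past healing

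*SAP*

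**What the plan says.** **The comparisons.** SAP 8.2.1 plans that "The number and percentage of subjects with an event by the internal Tactile AE codes will be compared by treatment group" (Table 14.3.2). It also plans an overall summary by severity, causality, outcome and seriousness. That shell is titled "Table 14.3.1 Safety Analysis: Summary Incidence of Adverse Events", with no time point, and its footnote reads "Denominator is the number of patients in the Safety Analysis Set". It reports Kruskal-Wallis p-values; the footnote to Table 14.3.2 reads "P-value calculated from CMH Test". Neither the text nor the shells give a start date, an end date, a treatment-emergent definition or person-time. By contrast, Table 14.3.3 (SAP 8.2.3) is fixed at 16 weeks, as are the Protocol safety endpoints (12.3.4).

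**The follow-up.** Protocol 5.3 states, for the time after healing: "All subjects assigned to the ACTitouch arm who heal during the 16 week treatment period will be followed for 3 months post VLU healing". They are told to keep using the device, and Protocol 6.6 has them seen monthly. For controls, Protocol 6.4 says: "Subjects will complete weekly visits for 16 weeks or until the VLU is completely healed". The Synopsis likewise limits follow-up to ACTitouch subjects who heal.

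**What can be counted.** Protocol 9.3 lists "New or worsening ulceration" among the pre-defined events reportable whatever their severity. Protocol 7.9 has new ulcers on the study limb traced for AE documentation throughout the study, and 6.8 provides a recurrence visit during follow-up.

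**The concern.** A percentage of subjects with at least one event grows with the time each subject is watched. Here that time depends on arm once the ulcer heals: roughly 13 further weeks for ACTitouch and none described for control. A post-healing event, of which a recurrent ulcer is the obvious example, can enter the ACTitouch count but has no counterpart in control. The p-values in these two tables would then partly test length of follow-up, and the gap would widen as more ulcers heal. SAP 8.2 says the group comparisons assess the significance of the difference between treatment and control, so readers will take the p-values as safety evidence. The primary endpoint is not affected.

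**Working it through.** The documents give no event rate, healing rate or exposure time, so there is no plan figure to reproduce. The question is what the two tables would show if both arms had the same true hazard.

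**From the documents:** 102 per arm (Synopsis); two-sided alpha 0.05 (Protocol 12.1); 16 weeks of treatment; 3 months, about 13.04 weeks, of extra observation for healed ACTitouch subjects only.

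**Assumed:** share healed *h* = 30-60%, the same in both arms; healing week *w* spread evenly over weeks 4 to 16 (mean 10); 16-week event risk *p* = 20% or 40%; constant hazard before healing; post-healing hazard equal to *r* times the earlier hazard, with *r* = 1, 0.5, 0.25 or 0; equal detection; unstratified two-proportion z-test.

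**Formulas:**
- Weekly hazard: λ = -ln(1 - p)/16.
- Non-healer, either arm: risk p.
- Healed control: mean over w of 1 - exp(-λw).
- Healed ACTitouch: mean over w of 1 - exp(-λ(w + 13.04r)).

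**One case in full (h = 50%, p = 20%, r = 1):**
- λ = -ln(0.8)/16 = 0.01395 per week.
- Mean observation: ACTitouch 0.5 × 23.04 + 0.5 × 16 = 19.5 weeks; control 0.5 × 10 + 0.5 × 16 = 13.0 weeks; ratio 1.50.
- Control incidence: 0.5 × 12.9% + 0.5 × 20% = 16.4%.
- ACTitouch incidence: 0.5 × 27.4% + 0.5 × 20% = 23.7%.
- Difference 7.2 points, ratio 1.44.
- Standard error under the null √(2 × 0.2007 × 0.7993/102) = 0.0561; under the alternative 0.0559. Chance of a significant result against ACTitouch: 1 - Φ[(1.96 × 0.0561 - 0.0724)/0.0559] = 25%, against a nominal 2.5%. A 20,000-run simulation gives the same 25%. With the arm sizes printed in the SAP's efficacy shells (122 and 128), it is 30%.

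**Two-sided false-positive rate, 102 per arm:**

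| Healed | 16-week risk | r = 1 | r = 0.5 | r = 0.25 | r = 0 |
|---|---|---|---|---|---|
| 30% | 20% | 12.1% | 7.0% | 5.5% | 5.0% |
| 30% | 40% | 19.3% | 9.3% | 6.2% | 5.0% |
| 45% | 20% | 21.3% | 9.6% | 6.2% | 5.0% |
| 45% | 40% | 37.3% | 14.9% | 7.7% | 5.0% |
| 60% | 20% | 34.0% | 13.4% | 7.3% | 5.0% |
| 60% | 40% | 59.0% | 23.1% | 10.0% | 5.0% |

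**Unequal detection (h = 50%, p = 20%).** Suppose ACTitouch picks up only a fraction of treatment-period events. At r = 1 and 60% detection, the incidence ratio is still 1.09. At r = 0.5 it is 1.05 at 80% detection and 0.96 at 70%.

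**After the fix.** Counting in both arms only to healing or week 16 gives 16.4% in each arm in the worked case, with simulated rejection of 2.4-2.5% in each direction.

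**The case against.** *The window may exist elsewhere.* The SAP calls itself abbreviated, starts at 8.1 and refers back to definitions that it does not contain. The schedule of activities is also not visible in the public text. A cutoff in the original SAP, or a week-16 contact for healed controls, cannot be excluded. This limits the claim to the supplied text. That text nevertheless specifies the tables to be produced, and it states a time point for Table 14.3.3.

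*The post-healing hazard may be low.* Infection, maceration and worsening ulceration largely need an open ulcer. This stands: the upper figures hold only if the hazard does not fall after healing, and at zero there is no bias.

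*Detection runs the other way during treatment.* Controls are examined weekly; ACTitouch subjects have seven visits plus text or phone contacts (Protocol 6.4, 6.5). This stands too. A reader might infer that equal true risk must appear as excess ACTitouch harm. The documents do not support that, because the net direction depends on both post-healing hazard and detection. Two opposing biases still do not make a valid test.

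*The pre-specified safety comparison already has a time point.* It does, in Table 14.3.3. A reader might want that table cut at healing as well, since its window is also unequal if healed controls go unobserved to week 16. Doing so would replace the Protocol's 16-week endpoint with a window ended by an efficacy outcome, which is debatable as a primary count.

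*Run-in events.* A reader might infer that counting them adds to the bias. They precede randomization and all subjects then wear bandages, so they add noise rather than a between-arm difference.

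*The bias works against the sponsor's device.* It therefore cannot create a false claim of safety through this route, and no decision rule rests on these p-values. That lowers the stakes but does not make the comparison interpretable.

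**Conclusion.** The point holds for Tables 14.3.1 and 14.3.2 as specified in the supplied SAP. They test crude subject percentages with no window and no person-time, over follow-up that differs by arm once a subject heals. The direction, inflated ACTitouch incidence, is conditional on some healing, a post-healing hazard above zero and equal detection. The documents fix the roughly 13 extra weeks; everything else about the size is assumed. Under the stated model the two-sided false-positive rate is about 12-59% at full post-healing hazard, 7-23% at half, 5.5-10% at one quarter and 5% at zero. The 12-59% range should not be quoted without its condition.

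**What to change.** For the between-arm p-values in Tables 14.3.1 and 14.3.2:
- Count only events with onset from randomization to the earliest of healed visit, exit or week 16, in both arms.
- Show person-weeks of observation by arm.
- Tabulate ACTitouch post-healing follow-up events separately, without a p-value.
- Put run-in events in a separate descriptive row.

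Keep Table 14.3.3 at the Protocol's 16-week endpoint and add the to-healing count there only as a sensitivity analysis. An event rate per person-week over all follow-up would not be enough by itself: if the hazard falls after healing, the extra ACTitouch weeks would dilute that arm's rate.

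The cost is SAP wording and a date filter; onset dates are already in Listing 16.2.7.1. There are two small downsides. Post-healing on-device events leave the comparative tables, though they are still reported. A window ended by healing is also shorter in an arm that heals faster, which is why person-weeks are shown. A slight imbalance remains because ACTitouch visits are more widely spaced: with healing spread evenly over weeks 4-16, it is noted on average 1.58 weeks late in ACTitouch and 0.50 in control, a difference of about 1.1 weeks per healed subject.

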8.2.2 Serious Adverse Events

SAEs will be listed, sorted by treatment group, subject identification, and onset date (Table 16.2.7.2). Data presented will include: causality, severity, seriousness, outcome, verbatim description, internal Tactile codes.

8.2.3 Other Safety Analyses

The following analyses will be carried out on the Safety Populations. ACTitouch® treated subjects will be compared with multi-layer bandaging treated subjects in terms of:

- the difference in the incidence of ulcer-related adverse events (defined as ulcer infections, maceration, allergic reaction to dressing, or hospitalization for worsening VLU) at 16 weeks using the Cochrane-Mantel-Haenszel (CMH) test (Table 14.3.3).

